5.3 Unscheduled Visits

All unscheduled visits will be included in care-time although no study questionnaires will be administered during visits not associated with immunotherapy infusions.

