- **Health related quality of life** : The Functional Assessment of Cancer Therapy-General (FACT-G) 27-item questionnaire will be used to measure four main domains of health related quality of life in cancer patients including physical, social, emotional and functional well-being⁴. The FACT-G takes approximately 5-10 minutes to complete. This will be completed at the time of enrollment and during each infusion visit.
- **Patient satisfaction**: The Patient Satisfaction Questionnaire-18 will be used to assess global satisfaction with medical care including six aspects of care: technical quality, interpersonal manner, communication, financial aspects of care, time spent with doctor, accessibility of care¹. The PSQ-18 takes approximately 3-4 minutes to complete. This will be completed at the time of enrollment and during each infusion visit.
- **Provider satisfaction**: The net-promoter score is a gauge of participant satisfaction taken by asking how likely they would be to recommend your service or program on a scale of 0-10^{2,3}. These will be completed at the time of study completion.

3.4 *Study Endpoints*

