3.4.2 Secondary Study Endpoints

AIM 2 Randomized control trial: Secondary endpoints will include total wait time (see attached study flowchart), total number of ED visits and/or hospitalizations, health related quality of life utilizing the FACT-G⁴, treatment satisfaction with the PSQ-18¹, and providers satisfaction using the net-promoter score^{2,3}.

4 Study Population and Duration of Participation

4.1 *Duration of Study Participation*

AIM 1 Pilot study: The duration of study participation will be 2 months from the date of enrollment.

AIM 2 Randomized control study: The duration of study participation will be the time it takes to complete 3 infusion visits, approximately 3 months..

4.2 *Total Number of Subjects and Sites*

Penn (Perelman Center for Advanced Medicine floors 2,3,4) will be the only site recruiting patients. For the pilot study we will enroll up to 100 patients over a 2-months. For the randomized control trial, to have 160 evaluable subjects, with an expected 10% drop out rate, we plan to enroll 176 patients.

4.3 *Inclusion Criteria*

AIM 1: Pilot participants:

- Over 18 years of age
- Access to mobile device with text messaging capabilities
- Receiving single agent PDL-1/PD-1 targeted immune checkpoint blockade for any solid malignancy
- Treating oncologist is at Penn's Abramson Cancer Center

AIM 2: Randomized control trial participants:

- Over 18 years of age

CONFIDENTIAL

- Receiving single agent PDL-1/PD-1 targeted immune checkpoint blockade for any solid malignancy
- Access to and ability to use a mobile phone with texting capabilities

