5.2.2 Randomized control trial

For patients in the intervention arm, symptoms (using the text-based e-triage) and laboratory results (see appendix B) will be assessed 96 hours prior to the intended infusion date. A standardized algorithm to assess each laboratory value and clinical question will be used to triage patients. Those with normal laboratory tests and no flagged symptoms will proceed to their infusion without an office visit, those with either abnormal laboratory tests or any flagged symptoms will proceed to an in-person provider evaluation prior to their infusion (see appendix A). Providers and patients will be offered the option to override the system and request in-person evaluation. Patients in the control group will be assessed with standard in-person assessment. Patient time will be collected using an in-house real time tracking system via Bluetooth technology. There will be no additional visits required outside of those necessary for routine cancer care.

CONFIDENTIAL

Patients will be monitored for effects on health-related quality of life and treatment satisfaction at the time of consent and during their infusion for each cycle for a total of 3 cycles of therapy. Data will be collected during this time given that majority of immune mediated toxicity occurs prior to this timepoint^{44,46,47}.

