5.2.3 End of Study Visit

The last visit will be during their final infusion during the follow-up window, at which time they will complete the FACT-G and PSQ-18 questionnaires as well as the opportunity to write an open-ended response regarding their experience with their program. At the same time, their physician will be asked to answer how likely they would be to recommend this program to a colleague on a scale of 1-10 through either email or EPIC inbox message according to physician preference.

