5.4 Subject Withdrawal

Subjects may withdraw from the study at any time without impact to their care. The investigator may withdraw subjects who violate the study plan, to protect the subject for reasons related to safety i.e. patients ability to safely and adequately execute the e-triage. It will be documented whether each subject completes the study. Subjects who withdraw early will have a final visit to collect final questionnaires and assess adverse events.

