10.2 Benefits

AIM 1 Pilot study: The benefit to participating in the pilot study is the advancement of knowledge regarding safe health-care delivery strategies that optimize the patient experience receiving cancer care.

AIM 2 Randomized control trial: The benefit of participating includes the potential to minimize the time burden associated with routine cancer treatment. For patients who are triaged to receive treatment earlier drug can be made in advance and patients will have the ability to optimize their infusion appointment timing to increase efficiency. The opportunity for participants to have more options for how they interact with the healthcare system, i.e., the choice whether to see a provider if they have normal laboratory testing and no treatment or cancer related symptomatology. The ability to identify treatment or cancer related adverse events earlier which could allow for earlier cancelations of unsafe infusion visits or the option to intervene and optimize patients for treatment earlier. Participants will be participating in a study designed to innovate cancer care delivery, ideally improving patient-centered care.

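### After enrolment, FACT-G and PSQ-18 are scheduled only at infusions, so scores are missing when a cycle is held and after immunotherapy stops without withdrawal

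*Protocol*

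**What the plan says.** Protocol section 3.3 (Study Measures) sets the same schedule for FACT-G and PSQ-18: "This will be completed at the time of enrollment and during each infusion visit". Section 5.2.2 repeats it as "at the time of consent and during their infusion for each cycle for a total of 3 cycles of therapy". Section 5.2.3 places the end-of-study set at the last infusion: "The last visit will be during their final infusion during the follow-up window, at which time they will complete the FACT-G and PSQ-18 questionnaires". Section 5.3 counts unscheduled visits in care time but states that "no study questionnaires will be administered during visits not associated with immunotherapy infusions".

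The exception is in section 5.4: "Subjects who withdraw early will have a final visit to collect final questionnaires and assess adverse events". Section 5.4.1 says much the same for those who withdraw consent. Section 7.4.2 also ends a patient's enrolment after an emergency needing intervention, and does not say whether final questionnaires then apply.

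Section 4.1 defines participation by infusions: "The duration of study participation will be the time it takes to complete 3 infusion visits, approximately 3 months". Protocol section 6.2 and SAP section 1.2 analyse both scores with a longitudinal linear mixed-effects model. Neither states how missing scores are handled, what is assumed about them, or any sensitivity analysis.

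**The concern.** The occasion for measurement depends on the patient's health. Section 7.1.1 recognises that immune-related events lead to treatment holds, and section 6.1 gives disease progression and change of therapy as reasons for drop-out. A new toxicity or progression can stop the infusion and lower quality of life at the same time, and it is then that no form is due. Section 5.2.2 justifies the collection window by saying that most immune toxicity falls inside it, yet the schedule pauses when toxicity interrupts treatment.

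The mixed model is valid when missingness depends only on scores already observed. That is doubtful if the event that removes the score also changes it. At stake is the reassurance in section 1.1 that care time can be cut while satisfaction and treatment outcomes are preserved. Burden from unscheduled visits is recorded, but the quality-of-life score that would sit beside it is not.

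**Working it through.** **Step 1. What each type of patient is scheduled to give.**

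| Situation | FACT-G and PSQ-18 under the plan | Protocol section |
|---|---|---|
| Three infusions as scheduled | Enrolment and all three infusions | 3.3, 5.2.2, 5.2.3 |
| Cycle held, later resumed | None at the held cycle; scores again on resuming | 3.3, 4.1, 5.3 |
| Immunotherapy stopped, still in study | Enrolment and infusions received; nothing scheduled afterwards | 3.3, 5.2.3, 5.3 |
| Withdraws early or withdraws consent | As above, plus a final questionnaire visit | 5.4, 5.4.1 |
| Enrolment ended after an emergency | Not stated whether the final visit applies | 5.4, 7.4.2 |

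The third row is the clear gap. A patient who leaves the study has a final form scheduled, while one who stays in it after stopping treatment does not. The second row loses one time point and the fifth is undefined.

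**Step 2. The plan's own figure.** The only power figure for the randomized trial concerns total care time: 80 per group, 130 versus 78 hours, SD 118, alpha 0.05 (taken as two-sided).

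- Standard error = 118 × √(2/80) = 18.66 hours.
- Standardised difference = 52 / 18.66 = 2.787.
- Power = Φ(2.787 − 1.960) = Φ(0.827) = 79.6%; the noncentral t calculation gives 79.1%.

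The stated 79% is reproduced. It does not involve FACT-G or PSQ-18, and section 5.3 keeps unscheduled visits in care time, so this point leaves it untouched. No precision or power is stated for the two questionnaires.

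**Step 3. How large a bias could be.** The documents give no count of held or stopped patients and no score difference, so the inputs here are assumptions. Let *f* be the fraction of an arm with a missing later score and *g* the amount by which missing scores fall below observed ones, in SD units, taken as the same in both arms. The full-arm mean is (1 − *f*) × observed mean + *f* × (observed mean − *g*) = observed mean − *f g*. So an observed-only arm mean is too high by *f g*, and the arm difference is off by (*f*₁ − *f*₂) × *g*.

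With *g* between 0.5 and 1.0 SD:

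- 10% versus 10% missing: each mean is too favourable by 0.05 to 0.10 SD; the arm difference is off by 0.
- 10% versus 20%: the difference is off by 0.10 × *g* = 0.05 to 0.10 SD.
- 10% versus 30%: the difference is off by 0.20 × *g* = 0.10 to 0.20 SD.

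These values are for a raw comparison of observed scores. A mixed model conditions on earlier scores and may remove part of the bias, so they are not estimates of the bias in the planned analysis.

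**The case against.** The strongest reply is that the plan loses less than it seems to. Both forms are completed at every infusion, so a patient who stops after the first or second has already filled them in at what proves to be the final infusion. Recognising that only in hindsight loses the open-ended item and perhaps the physician rating, but no FACT-G or PSQ-18 score. This stands: what is absent is a score after the stop.

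Three stronger conclusions are tempting, and the documents do not support them.

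- **A reader might infer that the comparison covers only patients well enough to be treated.** It does not. The mixed model can use enrolment and earlier infusion scores from patients who later stop, and held patients may score again on resuming.
- **A reader might apply the 10% drop-out rate and conclude that about 18 of 176 patients (176 × 0.10 = 17.6) are unmeasured.** That rate describes patients expected to leave the study, whom the section 5.4 final visit may cover. It does not count those who stop treatment and stay.
- **A reader might take section 10.2 as evidence that missingness will differ by arm.** It mentions "earlier cancelations of unsafe infusion visits", which concerns timing, not number. A control patient found unfit at the office visit also gets no infusion and no form, and the same sentence says that earlier optimisation for treatment is possible, which could reduce missed infusions.

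It is also fair that section 5.3 concerns forms given during visits, so it does not forbid text or telephone collection, and that these are secondary endpoints. But nothing in the plan schedules remote collection, and the withdrawal provision does not reach patients who stop treatment without withdrawing.

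**Conclusion.** The point holds as a cheap improvement limited to secondary endpoints. Followed as written, the plan leaves FACT-G and PSQ-18 scores missing at held cycles and after immunotherapy stops without withdrawal, plausibly not at random, and the mixed model may not correct for this. If the missing scores are worse than the model predicts, later arm means will be too favourable. With a similar score deficit in both arms, the arm difference is biased only if holds or stops differ by arm. The documents contain no evidence of such a difference and no count of affected patients, so the size is unknown; the SD ranges above rest wholly on assumed inputs. The primary endpoint and its 79% power are unaffected.

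**What to change.** - In Protocol sections 3.3, 5.2.2, 5.2.3 and 5.3, schedule FACT-G and PSQ-18 at the originally scheduled date of each of the three cycles, whether or not the infusion is given.
- Add one assessment at about three months for every randomized patient still contactable, and align the definition of participation in section 4.1 with it.
- When no infusion takes place, collect the forms by text link or telephone. Section 8.1 already enrols all subjects on WaytoHealth, and remote completion respects the undertaking in section 5.2.2 to require no extra visits.
- Reconcile sections 5.2.3 and 5.3 with 5.4, 5.4.1 and 7.4.2, stating whether stopping immunotherapy, or termination of enrolment after an emergency, triggers the final questionnaires.
- In Protocol section 6.2 and SAP section 1.2, run the mixed model on scheduled time, state the missing-data assumption, and add a sensitivity analysis for scores missing not at random, for example by lowering the unobserved scores by a range of amounts in each arm.

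The cost is protocol and SAP wording, a scheduled message for each missed infusion, and the three-month contact. The downside is that a minority of forms are completed remotely and not in the infusion suite. Scores not collected at the time cannot be recovered later.

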5.4 Subject Withdrawal

Subjects may withdraw from the study at any time without impact to their care. The investigator may withdraw subjects who violate the study plan, to protect the subject for reasons related to safety i.e. patients ability to safely and adequately execute the e-triage. It will be documented whether each subject completes the study. Subjects who withdraw early will have a final visit to collect final questionnaires and assess adverse events.

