3.3 Study Measures

AIM 1 Pilot study:

- **E-triage:** The e-triage will consist of 16 questions, modified from the validated NCI Pro-CTCAE™, which will be sent to patients via WaytoHealth®'s two-way texting system 96 hours prior to their scheduled immunotherapy infusion (see appendix B). Questions will pertain to common or emergent immune related adverse events as defined by the NCCN guidelines and two senior disease experts⁴²⁻⁴⁴. Patients will be prompted via text to measure the presence and severity of symptoms over the week prior. A final question will be included to capture any additional symptoms patients wish to disclose.
- **NCI Pro-CTCAE™:** A subset of patients may be asked to fill out a subset of the NCI PRO-CTCAE™, a set of validated questions for the collection of patient-reported outcomes to capture symptomatic adverse events in patients on cancer clinical trials, in order assess construct validity.
- **Definition of gold standard:** Patient reported toxicity captured by the text-based instrument will be compared to provider reported toxicity as documented in the EMR as the gold standard. To assess provider reported toxicity, standardized abstraction protocols will be developed by the PI and implemented by trained research staff.

AIM 2 Randomized control study:

- **Care time:** Care time will be defined as total time spent commuting to and receiving cancer care (including time spent obtaining labs). This will be captured using a combination of time-stamp information abstracted from AirFinder®, a real time patient located system deployed in the Perelman Cancer Clinics, and self-reported time for commuting and time spent obtaining local labs. Commute times will also be estimated using the patient's home address geocoded using ArcGIS software.
- **Emergency department and hospitalization rates:** Total number of emergency department visits and hospitalizations will be collected using data abstracted from the Penn electronic medical record during a 3 month follow-up window as well as through patient check-ins with study staff during routine infusion visits to account for care received outside the Penn system.

CONFIDENTIAL

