6.1 Sample Size and Power Determination

AIM 1 Pilot study: This protocol describes a cross-sectional study designed to investigate the operating characteristics of a text-based e-triage to capture patients experiencing immune-related adverse events against the gold standard of documented toxicity assessments in the EMR. Due to the granular nature of our e-triage questionnaire we believe a sensitivity of 95-100% is very reasonable to anticipate.

Results from the interim analysis including 48 patients are shown in Table 1. Median age was 68.5 (IQR 58-72), 58% were female, 88% white, and most patients either had thoracic (25%), genitourinary (27%), head/neck (15%), or skin (15%) cancers. 53.2% of patients had at least 1 toxicity related adverse event documented in the EMR. Sensitivity to identify at least one toxicity related adverse event was 100% (95% CI 0.863-1.00) aligning with our primary endpoint. Despite being at our target sensitivity we identified two underperforming questions (pain and rash) and therefore optimized the instrument creating a version 2 (see appendix). Assuming the sensitivity and prevalence are same as those in the preliminary data, a sample of 47 patients will produce adequate precision for the estimate for sensitivity, with the half width of the 95% confidence interval no larger than 7%.

AIM 2 Randomized control trial: We plan to enroll 176 patients and expect to have 160 patients left assuming a 10% drop out rate (e.g., due to disease progression and need to change therapy). Based on the preliminary data recently published by this group measuring total care time of patients treated at the Penn Abramson Cancer Center⁸, we expect the total care time in the control group to have a mean of 130 hours with a SD of 118. A sample size of 80 per group will provide 79% power to detect a 40% reduction in the total care time (130 vs. 78) assuming a type I error rate of 0.05.

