6.3.2 Analysis of Primary Outcome of Interest

The primary analyses will be Intent-to-Treat, with the primary outcome (total care time measured over three months) compared using a two-sample t test, or Wilcoxon test if normal distribution assumption is violated (see section 6.2).

7 Safety and Adverse Events

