7.4.2 Data and Safety Monitoring Plan

Overall data and safety will be monitored on an ongoing basis by the PIs and the study team. As needed, the investigators may decide to appoint an independent medical monitor to evaluate adverse events and make recommendations for continuing or stopping a trial. No interim analysis will be conducted.

Monitoring e-triage: All Waytohealth© interactions will be input into a flowsheet embedded into the patient's EMR and available to all study and clinical staff. All relevant persons will be notified via an EMR alert when any new information is entered. Dedicated research staff will be monitoring for inputs daily and will interphase with the research PI as well as clinical team as needed for unanticipated responses or symptoms. Any identified symptom will require the patient to have an in-person assessment with their routine clinical team. Clinical staff will be notified of the patient's triage status and offered the opportunity to mandate an in-person assessment regardless of the patient's triage status. A patient's enrollment in the study will be terminated if they experience an emergency medical situation requiring intervention or violate study protocol.

Monitoring clinical events: Research staff will see patients at each of their infusion visits. During this time, they will assess for any unidentified immunotherapy adverse events as well as screen for any emergency department visits or hospitalizations which occurred outside the Penn system. Additionally, research staff will receive EPIC alerts corresponding to any emergency department visits or hospitalizations.

8 Study Administration, Data Handling and Record Keeping

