8.2 Data Collection and Management

All study participants will be assigned a unique study ID. The Research Electronic Data Capture (REDCap) system will be used to autogenerate the participant identifier and track patient information. Data is encrypted to hide patient identifies (such as name, address, birth date, and phone number), allowing for the conducting of research without endangering subject's personal privacy. All clinical data is entered onto a web-enabled case report form using the REDCap platform. All patient data are "de-identified" such that each subject record will be labeled with only a study ID (no MRN, names, account numbers will be recorded). All clinical data will subsequently be entered into a REDCap clinical database.

All study participants will be enrolled on the Waytohealth platform where the e-triage instrument will be executed. All data at-rest is stored on encrypted disks using encryption keys managed by WaytoHealth®. Encrypted disks use AES encryption with a minimum of 256-bit keys, or keys and ciphers of equivalent or higher cryptographic strength. User passwords are never stored in clear text; they are "salted" and "hashed" to eliminate data leakage (See appendix C and section 8.1 for more on the data protections).

Patients will be tracked using blue-tooth technology while in the cancer clinic. The real-time tracking system will be executed using Link Lab's Air finder system. Only the patients deidentified research study ID will be used to link the patient and their tracked health-care time. Access to this information is visible only by the research team and will be stored on encrypted disk.

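### Section 5.4 allows withdrawal from the study over ability to use the e-triage, which only the intervention arm can trigger after randomization, and lists no further care time, so time saved could be modestly overstated

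*Protocol*

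**What the plan says.** Protocol section 5.4 permits the investigator to withdraw subjects who violate the study plan, or "for reasons related to safety i.e. patients ability to safely and adequately execute the e-triage". The withdrawal is from the study, not merely from fast-tracking.

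Section 5.2.2 applies the e-triage to the intervention arm only: "Patients in the control group will be assessed with standard in-person assessment".

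On what happens next, section 5.4 says: "Subjects who withdraw early will have a final visit to collect final questionnaires and assess adverse events". Section 5.4.1, which deals with data collection for withdrawn subjects, adds an open-ended question on why the patient stopped. Neither section mentions care time. Section 7.4.2 adds that a patient's "enrollment in the study will be terminated if they experience an emergency medical situation requiring intervention or violate study protocol".

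The primary endpoint (section 3.4.1) is cumulative care time over three months or at least three infusion visits. Sections 6.2 and 6.3.2, and SAP sections 1.2 and 1.3.2, call the primary analysis Intent-to-Treat. Neither document has a rule for missing or partial care time.

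Section 10.1 already gives a milder response to a related problem: a patient who leaves the questionnaire incomplete is not fast-tracked.

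**The concern.** After randomization this exit is open to one arm only. An Intent-to-Treat comparison needs the care-time total of every randomized patient, and the text does not provide for completing the totals of those who leave this way. It does not order that their care time be dropped, but it does not say that collection continues.

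The loss could not be fully repaired afterwards. Commute time could be estimated later from the "home address geocoded using ArcGIS software" (section 3.3), provided the visits are known. Time on site comes from live tracking: "Patients will be tracked using blue-tooth technology while in the cancer clinic" (section 8.2). If tracking stops, that part is gone.

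The likely direction favours the intervention. A patient who cannot use the e-triage would probably be seen in the office each cycle and have care time nearer to usual care. Leaving such patients out, or entering a shortened total, lowers the intervention mean in either case.

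**Working it through.** **Inputs from the documents** (Protocol 6.1, SAP 1.1): control mean 130 h, SD 118 h, intervention mean 78 h, 80 analysed per group, type I error 0.05. On attrition: "We plan to enroll 176 patients and expect to have 160 patients left assuming a 10% drop out rate". With 1:1 allocation, 88 are randomized per arm.

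**The plan's own figure.** Standard error of the difference = 118 × √(2/80) = 18.66 h. Target difference = 130 − 78 = 52 h. Two-sided power is 79.1% by the noncentral t distribution and 79.6% by the normal approximation. The stated 79% is reproduced, and this concern does not affect it.

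**Assumptions.** The documents give no rate of withdrawal on this ground.
- The share of the intervention arm affected is *f* = 2%, 5% or 10%, that is 88*f* = 1.8, 4.4 or 8.8 patients.
- Planned dropout for all reasons is (176 − 160)/2 = 8 per arm, or 8/88 = 9.1%, so 10% is an upper bound.
- Affected patients would average 130 h with full follow-up, and the rest 78 h.

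**Case A, affected patients excluded.** The as-randomized mean is (1 − *f*) × 78 + *f* × 130 = 79.0, 80.6 or 83.2 h. The observed mean is 78 h. Overstatement = *f* × 52.

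**Case B, counting stops after one of three equal cycles and the partial total is entered.** Each affected patient contributes 130/3 = 43.3 h instead of 130 h. Overstatement = *f* × 130 × 2/3.

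| *f* | A: hours | A: share of 52 h | A: in SE | B: hours | B: in SE |
|---|---|---|---|---|---|
| 2% | 1.0 | 2% | 0.06 | 1.7 | 0.09 |
| 5% | 2.6 | 5% | 0.14 | 4.3 | 0.23 |
| 10% | 5.2 | 10% | 0.28 | 8.7 | 0.46 |

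If counting stopped halfway instead, the overstatement would be *f* × 130 × 1/2 = 1.3, 3.2 or 6.5 h.

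**If there is no true effect.** Suppose everyone averages 130 h and the affected patients resemble the others. Exclusion then gives 130 − 130 = 0, so no bias. Truncation still lowers the intervention mean by the hours in column B. By the normal approximation with unchanged SD, a shift of 0.23 SE raises the two-sided error from 5% to about 5.6%, and a shift of 0.46 SE to about 7.5%.

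These are shifts in means. If the Wilcoxon test is used, which the plan allows, they do not translate directly.

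**The case against.** The strongest reply is that the harm needs several steps the plan does not prescribe. The investigator may withdraw a patient but need not. Care-time collection would then have to stop, and the patient be left out or entered with a partial total, despite an analysis labelled Intent-to-Treat. That is fair, but the label cannot supply hours that were not recorded, and the sections on withdrawal do not ask for them.

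Second, the clause may be meant for other settings. Section 5.4 also covers the pilot, where everyone receives the e-triage. Patients are also enrolled before randomization and must answer a screening text first (section 4.5), so some unsuitable patients will leave before any arm imbalance can arise. The sentence is awkward enough to be read as covering only plan violations that endanger the patient. These readings narrow the problem. None closes the exit after randomization, and answering one screening text does not show that a patient can complete a 16-question instrument each cycle.

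Third, a way of keeping the patient in the study already exists. An incomplete questionnaire stops fast-tracking (10.1), patients and providers can override the triage (5.2.2), and clinical staff can require a visit (7.4.2). This stands as a reason to expect few withdrawals, but section 5.4 does not say that it should be used instead of withdrawal.

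Fourth, the size. The 10% row exceeds the whole planned dropout of 8 per arm, and section 6.1 gives progression and change of therapy as the examples of dropout. The 2% row may be the most realistic. A patient fast-tracked before withdrawal would also average less than 130 h. Truncation can follow any early exit, and most other exits are open to both arms. All of this stands, and it is why the effect is called modest.

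**Conclusion.** The concern holds. After randomization, section 5.4 contains a ground for leaving the study that only the intervention arm can meet, and the text does not provide for completing those patients' care time. The primary Intent-to-Treat analysis could therefore lack the totals it needs, with a likely bias towards the intervention.

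The size is modest: about 1 to 5 h if affected patients are excluded and about 2 to 9 h if totals stop after one of three cycles, against a 52 h target and an 18.7 h standard error. This rests on an assumed 2% to 10% of the arm being affected and on a usual-care mean of 130 h for those patients. The lower end is more plausible given the safeguards. The change should be made because it is cheap and the bias runs one way, not because the trial's conclusion is likely to turn on it.

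**What to change.** In section 5.4, for the randomized trial, separate stopping fast-tracking from leaving the study:

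- A patient judged unable to use the e-triage safely or adequately reverts to office visits within the assigned arm, consistent with section 10.1.
- Collection of care time, emergency and hospital use, and questionnaires continues unless the patient withdraws consent.
- The patient is analysed as randomized, and the number of such patients is reported.

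In section 7.4.2, add a clause that inability to use the e-triage is not by itself a protocol violation that ends enrollment.

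The investigator keeps full discretion to stop fast-tracking for safety. The cost is a wording change in 5.4, one clause in 7.4.2 and slightly more data collection. The estimate of time saved may be less favourable.
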